### 5.0 Analysis Populations and Important Subgroups

### 5.1 Analysis Population

The Intent-to-Treat (ITT) Population is defined as all subjects who randomised at the Baseline visit. The ITT Population will be used for the efficacy analysis. Of note, the surgery-related endpoints during Periods B and C will be analysed among the subjects who undergo surgery. Subjects in the ITT population will be analysed by treatment group as randomised.

In order to evaluate the impact of major protocol deviations on the primary efficacy endpoints, additional sensitivity analyses may be performed on a Per-protocol Population, which excludes subjects with major protocol deviations that potentially affect the primary efficacy endpoints. If it is decided that this analysis should be performed, the criteria for exclusion of subjects from the Per-protocol Population will be fully defined in the classification plan and the exclusion of subjects from the Per-protocol Population will be finalized before blind break and before the database lock.

The Safety Population is defined as all subjects who are in the ITT Population and receive at least one dose of study drug. The Safety Population in each period will be used for safety analysis. Of note, the surgery-related safety endpoints during Periods B and C will be analysed among the subjects who undergo surgery. Subjects in the Safety Population will be analysed by treatment group as treated.

### 5.2 Subgroup

To evaluate the consistency of the efficacy over demographic and other baseline characteristics, summaries and analyses will be performed for selected subgroups for the primary endpoint and ranked secondary endpoints. The detailed subgroups will be outlined in Section 6.5 and Section 7.5.

### 6.0 Efficacy Analysis

#### 6.1 General Considerations

[figure not shown]
The efficacy analysis will be conducted among the ITT Population. A sensitivity analysis for the primary efficacy endpoint may also be conducted among the Per-protocol Population, if defined.

Categorical variables will be analysed using Cochran-Mantel-Haenszel (CMH) test, stratified by baseline Hurley Stage and anatomical location of the surgical. Continuous variables will be analysed using ANCOVA method, with treatment, baseline Hurley Stage, anatomical location of the surgical, and Baseline values in the model.

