5.5.3 Method of Assigning Subjects to Treatment Groups

The randomisation schedules will be generated at AbbVie before the start of the study and will be provided to the IRT vendor. Before the study site is initiated, the instructions for use of the IRT will be provided to the site. All subjects will be assigned a unique identification number by IRT as they are screened for the study. The subjects will be randomised centrally and stratified by Hurley Stage (II versus III) and anatomical location of the HS surgical site (i.e., axilla versus inguinal region) in a 1:1 ratio to either adalimumab or placebo at Day 1. The number of subjects in Hurley Stage III is not to exceed 50% of the total planned number of subjects (100 subjects). In addition the number of subjects with an AN count of 3 or 4 is not to exceed 40 (20% of the total planned number of subjects).

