8.1.4 Statistical Analyses of Efficacy

The efficacy analysis will be conducted in the ITT Population and PP Population, if defined.

Visit windows and the data handling convention for summarizing efficacy results will be defined in the SAP.

Missing data will be imputed using the following methods for the efficacy analyses in the ITT Population:

- **Non-Responder Imputation (NRI):** the NRI analysis will categorize any subject who has a missing value at a specific visit as non-responder for that visit. The NRI will be the primary approach in the analyses of categorical variables. For analyses up to Week 12, NRI will be applied using evaluations within the period.
- **Last Observation Carried Forward (LOCF):** The LOCF analyses will use the completed evaluation from the previous visit within the particular period for efficacy measures assessed to impute missing data at later visits in the same period. Baseline efficacy evaluations will not be carried forward. LOCF will be the primary approach in the analyses of continuous variables, and the secondary approach in the analyses of categorical variables.
- **As-Observed:** The As-observed analyses will not impute values for missing evaluations, and thus a subject who did not have an evaluation on a scheduled visit will be excluded from the As-observed analysis for that visit. As-observed analyses will be the secondary approach in the analyses of continuous variables.

Multiple Imputation (MI) for missing values will be performed for the primary efficacy variable.

Lesions that receive intervention (e.g., contained within the excised surgical specimen, protocol-allowed minor interventions including incision and drainage) will be counted as permanently present from the date of the intervention.

In order to evaluate the impact of major protocol violations on the results of the trial, efficacy assessments obtained after the start of a major protocol-disallowed treatment will be excluded from the analysis. Subjects will be counted as non-responders for the categorical variable from the date of the major protocol-disallowed treatment and have their LOCF for continuous variables. The exclusion of efficacy assessments will be determined via classification prior to the database lock.

Additional analyses may be performed for the primary efficacy variable adjusting for baseline covariates in addition to the stratification factors.

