8.2 Determination of Sample Size

The study is designed to enroll approximately 200 subjects. Assuming the true treatment difference in this study population is at least 20%, 100 subjects per arm will provide at least 80% power to detect the treatment difference at the alpha level of 0.05. The study also has at least 80% power to demonstrate the point estimate of the treatment difference of at least 15%.

The response rates observed in the combined PIONEER I and II studies (Studies M11-313 and M11-810, respectively) for the HiSCR at Week 12 were 50.6% and 26.8% in the adalimumab ew group and placebo group, respectively. Due to the potential differences between the population of moderate-to-severe HS patients who are surgical candidates and the general moderate-to-severe HS patient population, a conservative estimate of 20% treatment difference is used for the power calculation.

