#### 6.2 Primary Efficacy Analysis

The primary endpoint to assess the efficacy of adalimumab prior to surgery in subjects with moderate to severe HS is:

• Proportion of subjects achieving HiSCR at Week 12

The primary null hypotheses are that there is no difference in proportion of subjects who achieve HiSCR at Week 12, between the adalimumab and placebo treatment groups. The null hypotheses will be tested under a two-sided significance level of 0.05.

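### The primary HiSCR test leaves out baseline AN count; a pre-specified AN-adjusted risk difference may gain some precision and costs essentially no power

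*SAP*

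**What the plan says.** - **Primary test.** SAP 6.1: "Categorical variables will be analysed using Cochran-Mantel-Haenszel (CMH) test, stratified by baseline Hurley Stage and anatomical location of the surgical" (the word site is evidently missing at the end). Protocol 8.1.4.1 gives the same test and adds a 95% CI for the treatment difference. SAP 6.2 adds no covariate: "The null hypotheses will be tested under a two-sided significance level of 0.05".
- **Baseline AN is available.** Inclusion criterion 4 (Protocol 5.2.1) needs a Baseline AN count, and Appendix C schedules lesion counts at Baseline.
- **AN elsewhere in the plan.** Protocol 5.5.3 limits low counts: "the number of subjects with an AN count of 3 or 4 is not to exceed 40". SAP 6.5 has two AN subgroupings (5 or fewer, 6 to 10, 11 or more; and split at the median). The imputation model in SAP 4.7 includes the baseline count of each lesion type.
- **Continuous endpoints** are adjusted for their own baseline value (SAP 6.1).
- **Adjustment of the primary endpoint is optional.** Protocol 8.1.4: "Additional analyses may be performed for the primary efficacy variable adjusting for baseline covariates in addition to the stratification factors". No covariate is named, and Protocol 8.1.4.2 makes such results supplementary. The one logistic model that Protocol 8.1.4.1 does name for this endpoint controls for change in body weight, not for AN.

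**The concern.** HiSCR is built from lesion counts, yet the starting count is absent from its primary analysis. Scoring each subject against their own baseline does not fully remove dependence on that baseline. Counts are integers, so the AN criterion requires a fall from 3 to 1 (67%), from 5 to 2 (60%), but only from 4 to 2 (50%). Lesions that receive an intervention also stay in the count: with two treated AN lesions, a subject who started at 3 can no longer reach 1, whereas one who started at 10 can still reach 5.

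If baseline AN does predict HiSCR beyond Hurley stage and location, adjusting for it narrows the confidence interval and raises power without any new data. Naming the covariate in advance also settles which adjusted analysis is reported, which the optional wording leaves open.

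**Working it through.** **Inputs from the documents.** Allocation "in a 1:1 ratio to either adalimumab or placebo at Day 1"; "100 subjects per arm will provide at least 80% power to detect the treatment difference at the alpha level of 0.05"; "a conservative estimate of 20% treatment difference is used for the power calculation"; earlier HiSCR rates "were 50.6% and 26.8% in the adalimumab ew group and placebo group, respectively"; two-sided alpha 0.05.

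**Assumptions.** The pair of rates behind the power statement is not given, so I take 26.8% vs 46.8%, with 30.6% vs 50.6% and 40% vs 60% as the range. The prognostic strength of AN is not given either. I take R² from 0 to 0.20, or an odds ratio of 1 to 3 per SD of log AN.

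**Step 1: the plan's own figure.** Power = Φ{[Δ√n − 1.96√(2p̄q̄)] / √(p₀q₀ + p₁q₁)}, with Δ = 0.20 and n = 100.
- 26.8 vs 46.8: p̄ = 0.368, so (2 − 1.96 × 0.6820)/0.6672 = 0.994, power 84.0%.
- 30.6 vs 50.6: 82.6%.
- 40 vs 60: 81.2%.

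The stated minimum of 80% is met in each case. With a continuity correction, which the plan does not mention, the figures are 80.1%, 78.6% and 77.1%.

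**Step 2: analytic gain.** If AN explains a share R² of the outcome variance, n becomes n/(1 − R²) and the CI half-width is multiplied by √(1 − R²). At 26.8 vs 46.8 the unadjusted half-width is 1.96 × √(0.445152/100) = 13.1 points.

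| R² | Equivalent total N | Power | CI half-width (points) |
|---|---|---|---|
| 0 | 200 | 84.0% | 13.1 |
| 0.02 | 204 | 84.7% | 12.9 |
| 0.05 | 200/0.95 = 211 | 85.8% | 12.8 |
| 0.10 | 200/0.90 = 222 | 87.6% | 12.4 |
| 0.20 | 200/0.80 = 250 | 91.1% | 11.7 |

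**Step 3: simulation of the actual methods.** N = 200, 4,000 trials per row, 26.8% vs 46.8%, randomised 1:1 within the four Hurley-by-location strata. Baseline AN was skewed with a minimum of 3 and median 8, and its log correlated 0.35 with Hurley stage. The methods were the planned CMH; a CMH with AN (5 or fewer, 6 to 10, 11 or more) as a third factor, making 12 strata; and logistic models standardised to a risk difference with a robust SE, without and with log AN. The last column is the variance of the standardised estimate with AN relative to that without.

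| OR per SD | Planned CMH | 12-stratum CMH | Standardised, no AN | Standardised, with AN | Variance ratio |
|---|---|---|---|---|---|
| 1.0 | 84.6% | 82.8% | 84.8% | 84.8% | 1.005 |
| 1.3 | 84.0% | 83.0% | 84.2% | 84.7% | 0.995 |
| 1.5 | 83.9% | 83.8% | 84.1% | 86.0% | 0.984 |
| 2.0 | 85.2% | 86.1% | 85.5% | 88.0% | 0.922 |
| 3.0 | 86.7% | 89.1% | 87.1% | 91.7% | 0.856 |

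Gain over the planned CMH: 0.2, 0.7, 2.1, 2.8 and 5.0 points. Gain due to AN alone (standardised with minus without): 0.0, 0.5, 1.9, 2.5 and 4.6 points. Monte Carlo error on a single power near 85% is 1.96 × √(0.85 × 0.15/4000) = 1.1 points. The methods were run on the same simulated trials, so contrasts within a row are steadier than that.

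**Step 4: type I error.** With 26.8% in both arms, the planned CMH rejected in 4.7% to 5.2% of trials and the AN-adjusted risk difference in 5.0% to 5.7%. Monte Carlo error is 1.96 × √(0.05 × 0.95/4000) = 0.7 points, so all are close to nominal. A few tenths of a point of the apparent gain over CMH may reflect this small difference in level.

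**The case against.** The case for leaving the plan alone is strong in several parts.

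- **A reader might infer that the primary test demonstrably wastes power.** The documents do not support that. They give no association between AN and HiSCR, the endpoint is already relative to baseline, and with a weak association the gain is nil or under one point. This stands.
- **A reader might infer from the cap on AN 3 or 4 that the sponsor expects AN to drive response.** Protocol 5.5.3 gives no reason for the cap, which sits next to a cap on Hurley Stage III and may only shape the severity mix. The subgroups are there to check consistency of the treatment effect, which is a different question from prognosis. This stands.
- **The planned test is not in error.** It is valid, follows the randomisation and reaches its stated power. Chance imbalance in AN is already covered by the test's error rate and the confidence interval; it is not bias. Because additional analyses cannot replace the planned one, a late choice of covariates could not change the primary result. This stands; it could affect only the supplementary results.
- **AN is partly handled already**, through the imputation model, the subgroups and the optional adjusted analysis. The SAP (3.0) also defers detail to a supplement that is not available here. This stands in part: none of these puts AN into a named estimate of the primary effect, and that choice belongs in the SAP.
- **Changing the primary test is more than a SAP edit**, since Protocol 8.1.4.1 and the imputation analysis both specify CMH. This stands and is counted in the cost.

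**Conclusion.** The omission is a modest missed opportunity for precision, not a flaw in the planned test. Over the assumed range, adjusting for log AN adds about 0 to 1 point of power at an odds ratio up to 1.3 per SD, 2 to 3 points at 1.5 to 2.0 and about 5 points at 3.0. The analytic figures agree: 1.8 to 3.6 points at R² 0.05 to 0.10, and 7.1 only at R² 0.20. If AN is not prognostic, essentially nothing is lost.

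These sizes rest on an assumed prognostic strength, an assumed AN distribution and 26.8% vs 46.8% as the true rates. The form of adjustment matters more than the decision to adjust: taking AN as a third CMH factor costs about 2 points if AN is not prognostic (84.6% to 82.8%) and only breaks even at an odds ratio near 1.5.

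**What to change.** Before unblinding, add to SAP 6.2 a covariate-adjusted risk difference for HiSCR at Week 12. Fit a logistic model with treatment, Hurley stage, surgical location and log baseline AN count over all regions (the count HiSCR uses, not the non-surgical count used for eligibility). Standardise the predictions to a risk difference and give a 95% CI from a robust SE. Keep non-responder imputation as planned. Do not report the conditional odds ratio as the main effect, because the SAP hypothesis concerns a difference in proportions.

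Then choose one of two routes:

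1. Make this the primary estimate and test, with the stratified CMH as supporting. Protocol 8.1.4.1 and the analysis step of the multiple imputation in SAP 4.7 must then be aligned.
2. Keep CMH as the primary test and report this as the named adjusted risk difference and CI. State in advance that the CMH p-value and the CI may occasionally disagree, and that the p-value decides.

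Do not add AN as further CMH strata.

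Cost: no new data, a short SAP text and a few lines of code; under route 1, also a small protocol and SAP alignment. The downside is a model-based estimate in place of a simple stratified table. With about 100 × 0.268 + 100 × 0.468 = 74 expected responders and four model terms besides the intercept, the fit should be stable.

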#### 6.2 Primary Efficacy Analysis

The primary endpoint to assess the efficacy of adalimumab prior to surgery in subjects with moderate to severe HS is:

• Proportion of subjects achieving HiSCR at Week 12

The primary null hypotheses are that there is no difference in proportion of subjects who achieve HiSCR at Week 12, between the adalimumab and placebo treatment groups. The null hypotheses will be tested under a two-sided significance level of 0.05.

### 6.3 Secondary Efficacy Analysis

The following null hypotheses for ranked secondary endpoints below will be tested in a hierarchical order using two-sided significance level of 0.05 only if the null hypothesis for the primary endpoint has been rejected:

- 1. Adalimumab is not different from placebo with respect to the proportion of subjects achieving HiSCR-es at Week 12
- 2. Adalimumab is not different from placebo with respect to the proportion of subjects achieving HiSCR-es at Week 24
- 3. Adalimumab is not different from placebo with respect to the percent change in surface area of the HS surgical site from Baseline to Week 12
- 4. Adalimumab is not different from placebo with respect to the proportion of subjects at Week 12 that require a less extensive surgery than the surgical plan (determined at Baseline) or no surgery as determined by the designated surgeon

### 6.4 Other Efficacy Analysis

Other efficacy endpoints will be compared between the adalimumab and placebo treatment groups among the ITT Population.

### 6.5 Efficacy Subgroup Analysis

Primary and ranked secondary efficacy variables will also be analysed with respect to demographics and Baseline characteristics in addition to the stratification factors. The subgroups are defined as follows:

- Age group ( $< 40, 40 64, \ge 65$ , if less than 10% of subjects in the  $\ge 65$  group, that group will be combined with 40 64 group.)
- Sex (male, female)
- Race (White, non-White)
- Duration of HS (by median)
- Weight (by median);
- BMI category: normal (< 25), overweight (25 < 30), obese (30 < 40), Morbid obesity ( $\ge 40$ )
- Current smoking status at Baseline (yes, no)
- Baseline CRP level (by median)
- Baseline AN count ( $\leq 5, 6 10, 11+$ )
- Baseline AN count (< median, ≥ median)
- Prior HS surgery history (yes, no)
- Time from prior HS surgery to the first dose of study drug (< median,

   ≥ median)

## 7.0 Safety Analysis

#### 7.1 General Consideration

[figure not shown]
Safety analyses will include adverse events (AEs), laboratory, and vital sign measurements. Safety summaries will be provided using the safety populations.

Missing safety data will not be imputed.

### 7.2 Analysis of Adverse Events

Treatment-emergent adverse events (TEAEs) are defined as any event with an onset that is after the first dose of study drug and with an onset date within 70 days after the last dose of study drug in the analysis period, or prior to the first dose in the subsequent period for subjects who entered in to the subsequent period.

Pre-treatment AEs will be summarized separately.

All TEAEs, serious adverse events (SAEs), AEs leading to discontinuation and AEs of Safety Interest will be summarized. The number and percentages of subjects experiencing TEAE will be tabulated using the Medical Dictionary for Drug Regulatory Activities (MedDRA®) system organ class and preferred term.

Summaries (including percentages and event per 100 patient-year) of SAEs, deaths, AEs leading to discontinuation, and AEs of Special Interest will be provided as well. No statistical tests will be performed.

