6.1.4 Adverse Event Collection Period

All AEs reported from the time of study drug administration until either the final follow-up telephone call (approximately 70 days following discontinuation of study drug administration) or the date at which the subject initiated commercial adalimumab will be collected, whether solicited or spontaneously reported by the subject. In addition, SAEs and protocol-related nonserious AEs will be collected from the time the subject signed the study-specific informed consent. Adverse event information will be collected and recorded on the appropriate eCRFs.

Subjects will be contacted approximately 70 days following study drug discontinuation for an assessment of any new or ongoing AEs/AESI/SAEs as discussed in Section 5.3.1.1.

Adverse event information will be collected as shown in Figure 2.

Figure 2. Adverse Event Collection

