8.1.5 Statistical Analyses of Safety

All AEs, SAEs, AEs leading to discontinuation, pre-specified AEs of special interest (AESIs) and adverse events concerning the surgical site will be collected during the study and up to approximately 70 days after the last dose of the study drug for subjects who do not elect to treat his/her HS disease with commercial adalimumab.

Safety analyses will be carried out using the Safety Population. Pretreatment AEs will be summarized. Any TEAE is defined as an event with onset or worsening after the first study drug administration and within approximately 70 days after the last study drug administration for subjects who do not elect to treat his/her HS disease with commercial adalimumab.

The number and percent of subjects experiencing treatment-emergent TEAEs will be tabulated using the Medical Dictionary for Drug Regulatory Activities (MedDRA[®]) system organ class and preferred term. Comparisons of the percentages of subjects experiencing an AE in the adalimumab group versus the placebo group will be performed

using Fisher's exact test for data collected in the entire study, and separately for Period A, Period B, and Period C. Summaries (including percentages and event per 100 patient-years) of SAEs, deaths, AEs leading to discontinuation from the study, AESIs, and adverse events concerning the surgical site will also be provided.

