location of the surgical site (i.e., axilla versus inguinal region). A subject's Hurley Stage is determined by the worst Hurley Stage (i.e., II versus III) across all affected anatomic regions. The projected size of the surgical excision established by the designated surgeon during the Screening Period (calculated from a tracing of the outer perimeter onto an acetate sheet or equivalent) will be recorded by the study physician in the CRF. On each clinical study visit day, all study procedures scheduled for that visit will be completed prior to study drug administration.

[figure not shown]
**Period B:** A 2-week double-blind, placebo-controlled treatment period consisting of Weeks 13 and 14 (the peri-operative period) in which subjects will continue the treatment on the first day of Weeks 13 and 14. The designated surgeon will measure the surface area of the actual surgery and record in source document. Surgery will occur during Week 13. The surgery and post-operative management (e.g., hospitalisation, surgical wound care) will be as per local practice.

**Period C:** A 10-week double-blind, placebo-controlled post-operative treatment period will occur from Week 15 through Week 24, during which the subject will continue the treatment assigned at Day 1 from Week 15 through Week 23. No study drug will be administered at Week 24, the final study visit. Subjects may begin commercial product (as prescribed by the subject's physician) after all Week 24 procedures have been completed.

Subjects will be contacted approximately 70 days following study drug discontinuation for an assessment of any new or ongoing AEs/SAEs, except for those subjects who continue on adalimumab not supplied in the context of the clinical trial after the end of study participation. These subjects are not required to complete the 70-day follow-up telephone call and any new AEs should be reported through the mechanism used for all post-marketing adverse experience.

The schematic of the study is shown in Figure 1. Further details regarding study procedures are located in study protocol Appendix C.

[figure not shown]
Figure 1. Study Schematic

See Section 5.2 of the protocol for information regarding eligibility criteria. Study sites and subjects will remain blinded for the duration of the study.

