## 8.0 Summary of Changes

The following changes are made in SAP version 2:

• Clarified multiple imputation details in Section 4.7.

The following changes are made in SAP version 3, before the study database lock and before the study unblinding:

- Clarified that HS PGIC is assessed to validate skin pain only and will not be analysed in Section 4.3.3.
- Clarified that the flare endpoint, and the endpoint about at least 25% increase in each lesion type with a minimum increase of 2 relative to Baseline, will be analysed across all body regions and across body regions excluding the surgical site in Section 4.3.3.
- Clarified details about missing data imputation in Section 4.7.
- Emphasized that lesions removed by protocol allowed interventions will be treated as permanently existing in Section 4.7.
- Clarified that efficacy subgroup analysis will be performed on selected subgroups in addition to stratification factors in Section 6.5.
- Removed 'in each period' in Section 7.5 for clarification purposes, since there is only one study period for safety analysis.

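### SAP 7.2 keeps the treatment-emergent AE window open to 70 days after the last dose for every subject, while the protocol ends AE collection when commercial adalimumab starts

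*SAP*

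**What the plan says.** SAP 7.2 defines a TEAE as an event that begins once study treatment has started, dated as follows: "with an onset date within 70 days after the last dose of study drug in the analysis period". Its only earlier cut-off is "or prior to the first dose in the subsequent period for subjects who entered in to the subsequent period". SAP 8.0 explains an edit to the safety subgroup section by saying "since there is only one study period for safety analysis".

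The protocol is narrower:

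- Section 8.1.5, like the synopsis, describes the tail as "within approximately 70 days after the last study drug administration for subjects who do not elect to treat his/her HS disease with commercial adalimumab".
- Section 6.1.4 ends AE collection at the final telephone call, about 70 days after study drug stops, or at another date: "or the date at which the subject initiated commercial adalimumab will be collected".
- Section 5.1.1 allows commercial product once the Week 24 procedures are done. Section 5.5.1 places the last study injection at Week 23.
- Section 5.3.1.1 excuses subjects who continue on commercial adalimumab from the 70-day call and sends their new AEs to post-marketing reporting.

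SAP 4.2.1 repeats that last rule: "These subjects are not required to complete the 70-day follow-up telephone call".

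SAP 7.2 also plans percentages and events per 100 patient-years for SAEs, deaths, AEs leading to discontinuation and AEs of special interest. It does not define patient-years, and it states that no tests will be performed.

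**The concern.** The analysis window and the collection window should end on the same day. For switchers they do not. Commercial adalimumab is not study drug, so starting it does not move the last study dose. It is not a study period either, so the early cut-off in SAP 7.2 does not apply to it.

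Three things follow:

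1. For a switcher, most of the tail is unobserved but formally at risk. Missing safety data are not imputed (SAP 7.1), so in the percentages this time counts as event-free.
2. If patient-years are built from the same window, the denominator includes time in which no events could be collected.
3. If a post-switch event does reach the database, SAP 7.2 counts it under the study treatment. An event in a former placebo subject now on commercial adalimumab would be tabulated as a placebo TEAE.

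Safety is part of the primary objective, and switching is a choice made after randomisation that could differ between arms.

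**Working it through.** The plan gives no figure to reproduce. The check sets the rules side by side and then does the person-time arithmetic.

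**End of the AE window for a subject who starts commercial adalimumab**

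| Source | Rule |
|---|---|
| Protocol 6.1.4 | Collection ends at commercial start |
| Protocol 8.1.5, synopsis | 70-day tail stated for non-switchers only; no end date given for switchers |
| Protocol 5.3.1.1, SAP 4.2.1 | No 70-day call required; new AEs go to post-marketing reporting |
| SAP 7.2 | 70 days after last study dose |

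SAP 7.2 is the odd one out, and the SAP's summary of changes does not mention the departure.

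**Days involved, for a completer, counted from Baseline as day 0**

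- Last study dose, Week 23: 23 × 7 = day 161.
- End of SAP window: 161 + 70 = day 231.
- Week 24 visit on schedule: 24 × 7 = day 168.
- Tail observed before a switch right after Week 24: 168 − 161 = 7 days.
- Tail not collected: 70 − 7 = 63 days; 63/70 = 90% of the tail and 63/231 = 27.3% of the window.
- With the ±7-day visit window (protocol 5.1.1) and the last dose on schedule, the uncollected part runs from 56 days (56/231 = 24.2%) to 70 days (70/231 = 30.3%).

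**Effect on events per 100 patient-years**

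Assume that patient-years run to the end of the SAP window, that the event rate is constant, that post-switch events are not collected, and that a share *s* of subjects switch right after an on-schedule Week 24 visit. Then

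reported rate / true rate = (231 − 63*s*) / 231 = 1 − 0.273*s*

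| Assumed *s* | Ratio | Understatement |
|---|---|---|
| 25% | 0.932 | 6.8% |
| 50% | 0.864 | 13.6% |
| 80% | 0.782 | 21.8% |
| 100% | 0.727 | 27.3% |

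Equal shares in the two arms leave the rate ratio unchanged. If the arms differed as 50% and 80%, a true ratio of 1.0 would appear as 0.782/0.864 = 0.90, or its inverse, 1.10. The documents give no switching share, so these rows show a range and predict nothing.

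**The case against.** The strongest reply is that the harm is mostly blocked upstream. SAP 7.2 works on collected data, collection stops at commercial start, and new AEs in switchers go to another reporting system. With the protocol followed, TEAE counts would hardly change whichever end date the SAP used. That stands. A reader might infer that the placebo column will be filled with events on commercial adalimumab; the documents do not support this. It needs an event to enter the database despite the collection rule. That is possible, because the call is waived rather than forbidden and the AE footnote to protocol Appendix C gives 70 days without exception (while referring back to 5.3.1.1 and 6.1.4), but it is the lesser effect. Nor would such an event be counted by randomised assignment: SAP 5.1 analyses safety as treated, although a placebo subject would still appear under placebo.

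A second reply is that the SAP never says patient-years run to day 231. SAP 3.0 leaves further conventions to a supplement that is not available here. If person-time follows observed follow-up, the dilution is zero. This also stands, so the rate figures are conditional. A constant event rate is a simplification too, since the window spans surgery and an off-drug tail.

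A reader might extend the point to the 70-day laboratory cut-off in SAP 7.3. Appendix C schedules no laboratory tests after Week 24 or premature discontinuation, and the 70-day contact is a telephone call, so there is almost nothing for that cut-off to act on.

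Finally, with no tests on AEs, no formal safety comparison is at risk, and for completers the data through Week 24, including the surgical period, are unaffected. What the replies leave standing is the contradiction in the definition itself.

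**Conclusion.** SAP 7.2 contradicts protocol 8.1.5, the synopsis and protocol 6.1.4, and does not fit SAP 4.2.1. For a completer who switches right after an on-schedule Week 24 visit, about 63 of 70 tail days (27% of the 231-day window) lie inside the TEAE definition but outside AE collection. That follows from the documents' own schedule.

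The effect on reported rates is hypothetical. It is about 27% times the share switching, provided patient-years follow the stated window and the event rate is constant. A reader might infer that the rates will be understated or the comparison between arms biased. The documents support neither as a fact, because they give no switching share and no patient-year definition. The main consequence is unobserved time; misattribution is possible but secondary. Only descriptive safety summaries are touched.

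**What to change.** In SAP 7.2:

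1. End the TEAE window at the earlier of 70 days after the last study dose and the day before the first commercial adalimumab dose.
2. Define patient-years to the same date, or to the end of observed follow-up if that is earlier.
3. List any later events separately, outside the comparison of arms.
4. Report the number of switchers and the observed follow-up by arm. Ending the window at the switch does not equalise follow-up: an on-schedule completer who switches at Week 24 still contributes about 168 days against 231 for one who does not, so readers need this to interpret the percentages.

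The cost is SAP wording and some programming. Protocol 6.1.4 already makes the commercial start date the end of collection, so the rule needs no new concept, though the team should confirm that the date is held in the database. Compared with the full window, patient-years shrink slightly if few subjects switch and by up to about 27% if all completers switch right after Week 24. That reduction removes only time in which events were not being collected.
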